#### 10.2.5. Definition of Source Document

Original source documents include data and records, e.g., hospital records, medical notes, laboratory notes, evaluation checklists, pharmacy dispensing records, records kept at the pharmacy and at the laboratory, documentation of shipments. Note that, for this protocol, the volunteer participant data collection tool (i.e., the Memory Aid) is not considered a source document. Data reported in the eCRF derived from source documents should be consistent with the source documents or the discrepancies should be explained.

#### 10.3. Database Locking Procedures

- A final database lock for the primary analysis will occur after all participants have completed all follow-up visits, a case-by-case review of the severity of any AEs has been performed and finalized, all data anomalies have been resolved and monitoring is complete.
- Remaining immunology data will be maintained in a separate immunology database.

#### 10.4. Record Archival

The PI is responsible for retaining study records for a period of two years following the date that a marketing application is approved for the product or, if no application is to be filed or, if a file application is not approved, until two years after the investigation is discontinued and the FDA is notified. The Sponsor will be responsible for providing the site with date of vaccine approval or IND withdrawal.

These records are also to be maintained in compliance with IRB, state, and federal medical records retention requirements, whichever is longest. Storage of all trial-related documents will be such that confidentiality will be strictly maintained to the extent provided by federal, state, and local law.

#### 10.5. Screen Failures

If a participant signs the study-specific ICF, but is not randomized because of non-eligibility (a screen failure), the reason for his/her non-eligibility should be entered in the medical records/notes/charts. Also, a screening log must be kept. Data from participants who fail screening will not be recorded in the eCRF, with the exception of demographic data and the reason for screen fail.

#### 10.6. Protocol Deviations

A protocol deviation is any noncompliance with the clinical trial protocol, GCP, or site SOP requirements. The noncompliance may be either on the part of the participant, the PI, or the study site staff. As a result of deviations, corrective actions are to be developed by the site and implemented promptly.

These practices are consistent with ICH E6:

- Compliance with Protocol, Sections 4.5.1, 4.5.2, and 4.5.3.
- Quality Assurance and Quality Control, Section 5.1.1.
- Noncompliance, Sections 5.20.1 and 5.20.2.

It is the responsibility of the site to exercise continuous vigilance to identify and report deviations within five working days after identification of the protocol deviation, or within five working days of the scheduled protocol-required activity. All deviations must be promptly reported to Emmes and sponsor via the appropriate eCRF within the electronic data system.

All deviations from the protocol must be addressed in study participant source documents. Protocol deviations must be sent to UMB IRB per its guidelines. The site PI/study staff is responsible for knowing and adhering to UMB IRB's requirements.

#### 11. STUDY MONITORING

Sponsor monitoring responsibilities will be provided by The Emmes Corporation. A site initiation visit will be conducted prior to beginning the study, and monitoring will be conducted at initiation, during, and at closeout of the study by the study monitor or designee.

During the course of the study, the Emmes monitor will visit the clinical site at intervals to verify compliance to the protocol; check for completeness, accuracy, and consistency of the data and study product accountability; adherence to CFR, and any additional regulations and requirements, including GCP, of the conduct of clinical research. The monitor should have access to participant medical records, study product accountability and other study-related records needed to verify the entries on the eCRFs.

The PI and the monitor must agree to cooperate to ensure that any problems detected in the course of these monitoring visits, including eCRF completion and query resolution, are resolved in a predefined timeframe.

To ensure the quality of clinical data across all participants at the site, a clinical data management review will be performed on volunteer data received at The Emmes Corporation. During this review, participant data will be checked for consistency, omissions, and any apparent discrepancies. In addition, the data will be reviewed for adherence to the protocol and GCP. To resolve any questions arising from the clinical data management review process, data queries and/or site notifications will be sent to the site for resolution prior to the site's last monitoring close-out visit.

Essential documents must be filed in the site study file on an ongoing basis and available for review by the Emmes monitor. Monitoring visits will be performed according to the Clinical Monitoring Plan.

#### 11.1. Independent Auditing

The SIPL or PATH representatives may audit the study to ensure that study procedures and data collected comply with the protocol and applicable SOPs at the clinical site and The Emmes Corporation, and that data are correct and complete. The PI will permit auditors (employees of the Sponsor or an external company designated by the Sponsor) to verify source data validation of the regularly monitored clinical study. The auditors will compare the entries in the eCRFs with the source data and evaluate the study site for its adherence to the clinical study protocol and GCP guidelines and applicable regulatory requirements.

## 11.2. Regulatory Agency Auditing

The PI must be aware that representatives from regulatory authorities or the IRB may wish to inspect the eCRFs and associated study records. The PI will notify the Sponsor within 24 hours following contact by a regulatory agency. The PI and study coordinator must make the relevant records available for inspection and will be available to respond to reasonable requests and audit queries made by authorized representatives of regulatory agencies. The PI will provide the Sponsor with copies of all correspondence that may affect the review of the current study or his qualification as an investigator in clinical studies conducted by the Sponsor. The Sponsor will provide any needed assistance in responding to regulatory audits or correspondence.

## 12. OBLIGATIONS AND ROLES OF THE SPONSOR, PI AND STUDY PERSONNEL

This study will be conducted according to GCP and in accordance with all federal regulations regarding the protection of human participants in research including US 21 CFR Part 50 and US 21 CFR Part 312. The PI agrees to perform the research in strict accordance with this protocol, the International Council for Harmonisation (ICH) Guideline for Good Clinical Practice (E6), as well as in conformity with any federal, state, or local regulations regarding the conduct of clinical studies.

In addition, the PI must follow local and institutional requirements including, but not limited to, investigational product, clinical research, informed consent and IRB regulations. The Sponsor will provide notification to the PI of protocol and amendment approvals by regulatory authorities when applicable. Any modifications to the research protocol, the ICF, and/or the questionnaires or change in PI must be submitted to UMB IRB for review and approval prior to implementation. The

PI may deviate from the protocol without prior approval only when the deviation is necessary to eliminate an apparent immediate hazard to the participant.

The PI will notify UMB IRB of SAEs and protocol deviations according to UMB IRB requirements.

Any deviation to the protocol that may have an effect on the safety or rights of the participant, or the integrity of the study, must be reported to the Sponsor by the PI as soon as the deviation is identified. In that event, the PI will notify the Emmes/Sponsor immediately by phone, notify UMB IRB, enter the deviation into the appropriate eCRF, and confirm notification to the Sponsor in writing within ten working days after the change is implemented. All deviations will be noted in the continuing review report to and UMB IRB, the annual report to the Sponsor, and in the final study report for and UMB IRB.

Except where the PI's signature is specifically required, it is understood that the term "investigator" as used in this protocol and on the eCRFs refers to the PI or appropriate study personnel that the PI designates to perform a certain duty. The PI is ultimately responsible for the conduct of all aspects of the study. Sub-investigators or other appropriate study personnel are eligible to sign for the PI on designated eCRFs.

The Emmes medical monitor will be responsible for reviewing all serious and unexpected AEs and providing an unbiased written report of the event.

#### 13. ETHICAL CONSIDERATIONS AND INFORMED CONSENT

#### 13.1. Informed Consent Process

Before any study-related activities and in agreement with applicable regulatory requirements, the PI must ensure that the participant is fully informed about the aims, procedures, potential risks, and potential benefits of the study. The participant will be given the written, IRB approved ICF, allowed ample time to read the consent form, encouraged to ask questions about the study, have the questions answered and then be given time to decide if s/he would like to participate in the study. It will be emphasized that participation is voluntary, and that the participant has the right to withdraw from the study at any time without prejudice.

The PI or designee must obtain the participant's voluntary, personally signed and dated ICF before any study-related procedures. The original, signed ICF must be kept in the site study file.

#### 13.2. Risk/Benefit

No benefits can be guaranteed to participants for their participation in this research study.

#### **Risks from Vaccine**

As with all injectable vaccines, appropriate medical treatment and supervision should always be readily available in case of a rare anaphylactic event following the administration of the vaccine. The mainstay in the treatment of severe anaphylaxis is the prompt use of adrenaline, which can be lifesaving.

Post vaccination, the participant should remain under the observation of not less than 60 minutes for occurrences of immediate or early allergic reactions. Corticosteroids and antihistaminics should also be available in addition to supportive measures such as oxygen inhalation and intravenous fluids (IV fluids).

This being a Phase 1 trial there is no safety data available with the use of MCV-5 vaccine. This trial aims to generate the same.

In clinical trials of Menactra®, most commonly reported injection site reactions following vaccination among adults were injection site pain (53.9%), induration (17.1%), redness (14.4%) and swelling (12.6%). In the same population, commonly reported systemic reactions were headache (41.4%), fatigue (34.7%), malaise (23.6%), arthralgia (19.8%), diarrhea (16.0%) and anorexia (11.8%), chills (9.7%) and vomiting (2.3%). All these are the frequencies reported within seven days of single vaccine dose. SAEs occurred in these individuals at a rate of 1.0% following Menactra® vaccine.

It is expected that the solicited reactions with adjuvanted and non-adjuvanted MCV-5 would be consistent with those reported in clinical trials of Menactra®.

#### Risks from blood draw

Drawing peripheral blood can cause discomfort; it might cause minor bleeding and/or bruising where the needle enters the skin, and very rarely might cause infection. This risk will be mitigated by ensuring that only study staff members who are adequately trained in safe drawing of blood conduct this portion of the study. It is not anticipated that the risks in any one of the vaccine groups would be higher than others.

#### Risks from participating in a clinical trial

In addition to the risks described above, all clinical trial participants are likely to experience increased inconvenience due to the visits as they may be of longer duration than standard treatment, which might cause more anxiety. They also incur additional risks to their privacy from participating in a clinical trial. This risk will be minimized by ensuring that participant confidentiality is maintained by enforcing appropriate data collection, storage, and analysis techniques and employing the use of unique identifiers with carefully stored linking files. There may be additional risks to study trial participation that we do not know about.

#### 13.3. Protocol Review Process

Scientific review of this protocol will be conducted by PATH, the sponsor of the study. The protocol will be submitted under a new IND. Protocol ethical review and oversight will be performed by UMB IRB. Continuing review will be undertaken in accordance with existing regulations. The Sponsor will be responsible for trial registration at ClinicalTrials.gov.

Copies of the approved continuing review and final study reports, along with the respective local IRB approval notifications, will be submitted to the Sponsor as soon as these documents become available.

## 13.4. Participant Confidentiality

The PI must ensure that participant confidentiality is maintained. Personal identifiers will not be included in any study reports. All study records will be kept confidential to the extent provided by national and local laws.

All study procedures will be conducted per GCP guidelines, and every effort will be made to protect participant privacy and confidentiality to the extent possible.

All study-related information will be stored securely at the study site or at a designated, secure off-site location. When not in use and under immediate control of study staff, all participant information will be stored in locked areas with access limited to study staff. Data collection, process, and administrative forms, laboratory specimens, and other reports will be identified exclusively by a coded number to maintain participant confidentiality. All local databases will be secured with password-protected access systems. Participants' study information will not be released without their written permission, except as necessary for monitoring or compliance with legal or regulatory requirements.

Medical records containing identifying information may be made available for review when the study is monitored by the sponsor or an authorized regulatory agency. Direct access may include examining, analyzing, verifying, and reproducing any records and reports that are important to the evaluation of the study.

#### 13.5. Reimbursement

Pending IRB approval, participants will be compensated for their time and effort in this study, and be reimbursed for travel to study visits. The study ICF will state the plan for reimbursement. Study participants will not be charged for study vaccinations, research clinic visits, research-related examinations, or research-related laboratory tests.

#### 13.6. Storage of Specimens

Stored study research samples (including samples retained for elective analysis) will be labeled by a code that only the study site can link to the participant. All stored research samples will be logged into a secure database and any use documented. Samples may be stored at several different repositories and laboratories to complete the analyses required to meet study primary, secondary and exploratory analyses. As a part of the informed consent process, participants will be informed of and asked to agree to long-term storage of specimens for use in future, related research.

#### 14. **APPENDICES**

#### 14.1. APPENDIX I: Schedule of Events

Study visit	Visit 1 / screening	Visit 2	Visit 3	Visit 4	Visit 5	Final Study Contact
Study Day	D -28 to-1	$D_1$	D 8+3	D 29+14	D 85+14	D 180±21
Informed Consent	$\sqrt{}$	-	-	-	-	-
Demographics	$\sqrt{}$					
Medical history	V	√A	√A	√A	√A	(For SAEs)
Prior and concomitant medications	~	$\checkmark$	$\sqrt{}$	V	(For SAEs)	(For SAEs)
Physical examination	$\sqrt{}$	√B	√B	√B	√B	-
Pregnancy test F (female only)	~	~		√	√	-
Vital signs	√	$\sqrt{}$	$\sqrt{}$	V	$\sqrt{}$	-
Safety laboratory evaluation c	10 mL	-	8 mL	-	-	-
Screening for HIV, hepatitis B and C D	8 ml					-
Eligibility criteria	√	V	-	-	-	-
Randomization of eligible participants	-	$\checkmark$	-	-	-	-
Vaccination	-	$\sqrt{}$	-	-	-	-
Visual inspection of injection site		$\checkmark$	$\sqrt{}$			-
Memory card review and collection	-	V	V		-	-
Observe for 60 minutes: Assess and record post vaccine reactions	-	V	-	-	-	-
Immunogenicity Blood collection	-	20 mL E		30 mL	-	-
Cumulative blood volume	18 mL	20 mL	8 mL	30 mL		
Adverse event reporting		Solicited local and systemic reactions  Adverse Events				
		Serious Adverse Events				

- A. Updated medical history only
- B. Targeted physical examination, as indicated
  C. Complete blood count (CBC): WBC, Hemoglobin, Platelets, Chemistry panel: ALT, Creatinine, Albumin, Total bilirubin
  D. HBsAg, anti-HCV (if positive, by PCR), HIV EIA
- E. Before vaccination
- F. Only in case of female participants with child bearing potential. At the time of screening a serum pregnancy test will be performed whereas on the day of vaccination, urine or serum pregnancy test will be performed

Study Protocol: ACYWX-001/VAC 046 Version 4.0: 27 September 2016

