#### STUDY PROCEDURES & VISIT SCHEDULE

After volunteers have signed the written informed consent, they will be screened for eligibility into the study. Screening will take place within 28 days prior to vaccination (Visit 1; Screening). A blood sample (up to 18 mL) will be taken at the screening visit for laboratory testing.

The following assessments will be conducted during the screening visit: medical history, physical examination, vital signs measurement and laboratory evaluation including hematology, serum chemistry and viral serology for Human immunodeficiency virus (HIV), Hepatitis B virus (HBV), and Hepatitis C virus (HCV). A test for pregnancy will be performed among females of child bearing potential. Inclusion/exclusion criteria will be assessed for eligibility.

At Visit 2 (Vaccination), eligible volunteers will be randomized in a 1:1:1 ratio to either one of the following groups:

Group	Vaccine
1 (n=20)	Adjuvanted Study vaccine (MCV-5)
2 (n=20)	Non-adjuvanted Study vaccine (MCV-5)
3 (n=20)	Reference vaccine (Menactra®, ACYW)

Baseline blood sample (20 mL) for immunogenicity testing will be collected before randomization on the day of vaccination and thereafter vaccine will be given as a single intramuscular injection of 0.5 mL in the deltoid. The day of vaccination will be considered as Day 1. After vaccination, participants will be observed for 60 minutes at the clinic to detect any immediate reactions or any other AE. All relevant information will be reported in the Case Report Form (CRF). A Memory Aid will be distributed and participants will be instructed to record post-immunization reactions, adverse events and concomitant medications. Participants will be informed to return to study centre for Visit 3 (Day 8).

At Visit 3 (Day 8), participants will undergo a targeted physical examination, vital sign measurement and a blood sample will be collected (up to 8 mL) to repeat the safety laboratory evaluations. Memory Aid records will be discussed with the participants, if needed, reconciled by the investigator/designee before recording in source document and transcribed into the CRF.

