At Visit 4 (Day 29), the participants will undergo a targeted physical examination, vital sign measurement and review of interim health history, medication use and any report of adverse event through personal interview. A blood sample (30 mL) will be collected for immunogenicity evaluations. All the relevant information will be recorded into the CRF. The participant will be informed of the Visit 5 schedule.

At Visit 5 (85 days after vaccination), the participants will undergo targeted physical examination and review of interim medical history including medication use. All serious adverse events will be recorded into the CRF by the investigator/designee.

At Final study contact (180  $\pm$  21 days after vaccination), the participant will be contacted by telephone to assess any serious adverse events that may have occurred.

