#### 2.4.4. Primary Endpoints

- The occurrence and severity of solicited local and systemic post immunization reactions within seven days following vaccination.
- The occurrence, severity, and relatedness of unsolicited adverse events for 28 days following vaccination, and serious adverse events for 6 months following vaccination.

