## 5.2.5. Visit 3 (Day 8 +3 days)

Study Protocol: ACYWX-001/VAC 046

On the eighth day after vaccination, the participant will return to the study site for the following procedures:

- a) Study staff review and record participant's interim health history, medication use and self-assessment experience through personal interview, assisted by the Memory Aid.
- b) Vital signs, injection site, and a targeted physical examination (if indicated) will be performed.
- c) Local and systemic reactions and AEs review as recorded in Memory Aid as well as asked for by PI (or designee). The highest temperature written in the Memory Aid each day will be recorded to source document as peak temperature.
- d) Findings of PI or study staff that suggest inaccuracy of reported self-assessments will be clearly documented.
- e) Any topics or new information considered by PI to be important to continued informed consent will be shared with the participant.
- f) Blood samples (8 mL) will be obtained for safety laboratory tests (Appendix I).
- g) Study staff will instruct the participant regarding continued self-assessment and need to contact study staff (a) in follow-up of specific AEs, (b) if injection site changes worsen or do not resolve, (c) if systemic symptoms worsen or do not resolve, and (d) if other AEs occur.
- h) The next visit is scheduled.

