- Questioning the participant, which should be done in an objective manner.
- Receiving an unsolicited complaint from the participant.
- Review of medical records/source documents.

Each participant will have a scheduled observation following vaccination, including a symptom-directed physical examination, if indicated. They will be monitored in-house for 60 minutes after vaccination. On Days 1 to 7 after vaccination, participants will be instructed to assess and record daily in a participant memory aid any signs and symptoms at the injection site, as well as systemic signs and symptoms. Follow-up visits will be conducted seven days after vaccination, including directed assessment, safety tests and verification of memory aid notes. They will be instructed to call the study team if they observe significant injection site or systemic signs or symptoms, and then to continue monitoring and reporting their condition. All participants will be followed for safety for six months after the vaccination.

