#### 3.2 Endpoints

#### 3.2.1 Primary Endpoints

- The occurrence and severity of solicited local and systemic post immunization reactions within seven days following vaccination.
- The occurrence, severity, and relatedness of unsolicited adverse events for 28 days following vaccination, and serious adverse events for 6 months following vaccination.

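### No written aid is specified for unsolicited AEs after Visit 3, so for 64-75% of the 28-day primary window capture rests on participant-initiated contact and an interview at Day 29-43

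*Protocol*

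**What the plan says.** Protocol 2.4.4 makes the "relatedness of unsolicited adverse events for 28 days following vaccination" part of the second primary endpoint, and SAP 3.2.1 repeats it ("unsolicited adverse events for 28 days following vaccination").

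The Memory Aid is handed out on Day 1. According to the synopsis (Study Procedures & Visit Schedule), "participants will be instructed to record post-immunization reactions, adverse events and concomitant medications", so it is meant for unsolicited AEs and medications as well as solicited reactions. Protocol 8.7 gives the recording period: "On Days 1 to 7 after vaccination, participants will be instructed to assess and record daily in a participant memory aid". At Visit 3 (Day 8 to 11), Protocol 5.2.5 has staff interview the participant with the Memory Aid's help and review the AEs written in it. Item (g) then says "Study staff will instruct the participant regarding continued self-assessment" and asks participants to contact staff about specific AEs, symptoms that worsen or persist, and any other AE.

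In Appendix I the row "Memory card review and collection" is ticked at Visits 2 and 3. The Visit 4 cell is blank, and Visit 5 and the final contact show a dash. Visit 4 falls on Day 29 to 43. Protocol 5.2.6 lists AE evaluation there without mentioning the Memory Aid, and the synopsis describes "review of interim health history, medication use and any report of adverse event through personal interview".

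Two analysis rules bear on the point. SAP 9.4.3 tabulates unsolicited AEs by Days 1-8 and Days >8. Protocol 7.5.2 and SAP 6.5 impute an AE start date with a missing day to the date of the last vaccine dose, which in this single-dose trial is the vaccination date.

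**The concern.** The written prompt covers the first week of a four-week endpoint. Participants are asked to go on assessing themselves after Visit 3, but no section gives them anything to write on, and no section has Visit 4 staff look at a written record. No contact is scheduled between the two visits.

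The events most likely to slip through are mild and short ones that a participant does not think worth a call. Onset dates are also at risk. They decide which side of Day 8 an event falls on and, because Visit 4 may be as late as Day 43, whether it belongs to the 28-day window. Protocol 5.5.7 also requires medication start and end dates up to four weeks after vaccination, and those face the same difficulty.

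At stake are the absolute AE rates of a first-in-human trial whose stated purpose is descriptive, and the reading of the SAP tables by period. A lower rate after Day 8 could come from the vaccine's true profile or from the change in how events are found, and the tables could not tell the two apart.

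**Working it through.** **Step 1. The plan's own figures (Protocol 7.4, SAP 5; n = 20 per group).**
- Chance of at least one AE at a true rate of 11%: 1 − (1 − 0.11)^20 = 0.9028. The plan says greater than 90%. Reproduced.
- One-sided 95% upper bound for 0 of 20: 1 − 0.05^(1/20) = 0.1391. The plan says approximately 14%. Reproduced.

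Both figures treat every event that occurs as recorded.

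**Step 2. Share of the window after Visit 3.** Visit 3 is on Day 8 to 11 (Protocol 5.2.5). Share = (29 − Visit 3 day) / 28.
- Visit 3 on Day 8: 21/28 = 75%.
- Visit 3 on Day 11: 18/28 = 64%.

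**Step 3. Gap between visits, and lag for an event.** The gap runs from 29 − 11 = 18 days to 43 − 8 = 35 days. The lag from an event's onset to the Visit 4 interview is a different quantity. For onsets from Visit 3 to Day 29:

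| Visit 3 | Visit 4 | Lag, days | Mean lag |
|---|---|---|---|
| Day 8 | Day 29 | 0-21 | 10.5 |
| Day 11 | Day 29 | 0-18 | 9.0 |
| Day 8 | Day 43 | 14-35 | 24.5 |
| Day 11 | Day 43 | 14-32 | 23.0 |

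**Step 4. Illustration of size.** The documents give no capture rate. Let c be an assumed capture of AEs after Visit 3, with full capture before it, onsets spread evenly over 28 days, and share f from Step 2. Then:
- overall capture = (1 − f) + f·c
- chance of observing an 11% AE = 1 − (1 − 0.11 × overall capture)^20
- true rate excluded by 0/20 = 0.1391 / overall capture

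For f = 0.75 and c = 0.80: overall capture = 0.25 + 0.75 × 0.80 = 0.85; chance = 1 − (1 − 0.0935)^20 = 86.0%; bound = 0.1391 / 0.85 = 16.4%.

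| Assumed c | Chance, f = 75% | 0/20 bound, f = 75% | Chance, f = 64% | 0/20 bound, f = 64% |
|---|---|---|---|---|
| 100% | 90.3% | 13.9% | 90.3% | 13.9% |
| 90% | 88.3% | 15.0% | 88.6% | 14.9% |
| 80% | 86.0% | 16.4% | 86.7% | 16.0% |
| 70% | 83.2% | 17.9% | 84.4% | 17.2% |
| 50% | 75.9% | 22.3% | 78.8% | 20.5% |

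**Step 5. Effects that need no assumed rate.** The SAP's cut between Days 1-8 and Days >8 lies almost exactly where Memory Aid support stops, so the two columns differ in ascertainment as well as in time since vaccination. An event from, say, the third week whose onset day is forgotten is dated to the vaccination day and counted in Days 1-8. Loss of late events and this imputation push the comparison in the same direction, towards early onset.

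**The case against.** A reader might infer that the diary is taken away at Visit 3, that everything afterwards depends on unaided recall over 18 to 35 days, and that AEs will certainly be under-counted. The documents do not support that reading.

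- **There is a prospective route.** Protocol 5.2.5 (g) tells participants to contact staff if other AEs arise. Section 5.2.4 supplies telephone numbers, 5.3 allows unscheduled visits, and 8.7 asks for calls about significant symptoms. This stands, and it rules out calling the capture unaided recall. It still depends on the participant choosing to call, and the 8.7 instruction is limited to significant symptoms.
- **Collection at Visit 3 is an inference from one table row.** The same row is ticked at Visit 2, when the Memory Aid is issued. The Visit 4 cell is blank rather than dashed, and the Visit 3 text speaks of review only. This stands. The gap does not depend on it, because entries are specified only to Day 7 and Visit 4 has no review step.
- **Eighteen to 35 days is the gap between visits.** Individual lags run from 0 to 35 days (Step 3).
- **Onset dates matter less for the overall counts.** SAP 9.4 includes all reported AEs, and the unsolicited rows in 9.4.1 apply no explicit onset filter. This holds for the overall summary. It does not hold for the Days 1-8 versus >8 tables, and Protocol 7.3.1 does define the rates over 28 days.
- **Decision impact is limited.** Participants and safety assessors are blinded and all arms share one process, so any loss is probably similar across arms. Solicited reactions lie within the Memory Aid period. Both points stand; what remains is an effect on absolute unsolicited rates.

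**Conclusion.** The point holds as a gap in ascertainment, worth closing because it is cheap to close. For 64-75% of the 28-day unsolicited-AE window the protocol specifies no written record, and capture rests on participant-initiated contact plus an interview at Day 29-43. Mild, brief events and exact onset dates in that period may be captured less completely. A between-arm bias is not shown and, given the blinding, is unlikely. The exposed results are the absolute unsolicited AE rates and the SAP's tables by period, where a change in method coincides with the cut point and forgotten onset days move to the vaccination date.

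The size of any loss cannot be derived from the documents. The shift from 90.3% to 86.0%, and of the 0/20 bound from 13.9% to 16.4%, rests on an assumed 80% capture after Day 8, even onset over 28 days and full capture before Day 8. It shows sensitivity and is not an estimate for this trial. A certain under-count cannot be claimed.

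**What to change.** - **Protocol 5.2.5, 8.7 and Appendix I:** review the Memory Aid at Visit 3, but have participants keep, or be reissued, the unsolicited-AE and medication pages through Day 29. State the longer recording period in 8.7, where only Days 1 to 7 now appear.
- **Protocol 5.2.6 and Appendix I:** add review and collection of the Memory Aid at Visit 4, in support of the AE interview. Its status under 10.2.5 (not a source document) need not change, because it would serve as a prompt, as it does at Visit 3.

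Cost: wording changes to the protocol and the Memory Aid, and a few minutes at a visit already scheduled. No extra visit or staff is needed. The downside is a small added burden on participants and possibly more minor AEs to code.
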